5.4 Screen Failures

Screen failures are defined as participants who consent to participate in the clinical study, but are not subsequently randomized in the study. A minimal set of screen failure information is required to ensure transparent reporting of screen failure participants to meet the Consolidated Standards of Reporting Trials (CONSORT) publishing requirements and to respond to queries from regulatory authorities. Minimal information includes demography, screen failure details, eligibility criteria, and any AEs or SAEs meeting reporting requirements as outlined in the data entry guidelines.

5.5 Participant Replacement Strategy

Any participant who discontinues from study intervention OR withdraws from the study will not be replaced.

6 STUDY INTERVENTION

Study intervention is defined as any investigational intervention(s), marketed product(s), placebo, or medical device(s) intended to be administered to a study participant according to the study protocol.

Clinical supplies (study interventions provided by the Sponsor) will be packaged to support enrollment as required. Clinical supplies will be affixed with a clinical label in accordance with regulatory requirements.

6.1 Study Intervention(s) Administered

The study interventions to be used in this study are outlined in [Table 3](#).

Table 3 Study Interventions

Arm Name	Arm Type	Intervention Name	Type	Dose Formulation	Unit Dose Strengths	Dosage Level(s)	Route of Admin	Treatment Period	Use	IMP or NIMP/AxMP	Sourcing
Group 1 (Run-in Period)	Experimental	MK-3655 Matching Placebo	Drug	Vial	0 mg	2 x 1.5 mL injections once	SC	V4 up to V5 (Run-in Period)	Placebo	IMP	Provided centrally by the Sponsor
Group 1	Experimental	MK-3655 33.3 mg/mL	Drug	Vial	50 mg	1 x 1.5 mL injection Q4W	SC	V5 to V15 (Double-Blind Treatment Period)	Test Product	IMP	Provided centrally by the Sponsor
Group 1	Experimental	MK-3655 Matching Placebo	Drug	Vial	0 mg	1 x 1.5 mL injection Q4W	SC	V5 to V15 (Double-Blind Treatment Period)	Placebo	IMP	Provided centrally by the Sponsor
Group 2 (Run-in Period)	Experimental	MK-3655 Matching Placebo	Drug	Vial	0 mg	2 x 1.5 mL injections once	SC	V4 up to V5 (Run-in Period)	Placebo	IMP	Provided centrally by the Sponsor
Group 2	Experimental	MK-3655 33.3 mg/mL	Drug	Vial	100 mg	2 x 1.5 mL injections Q4W	SC	V5 to V15 (Double-Blind Treatment Period)	Test Product	IMP	Provided centrally by the Sponsor
Group 3 (Run-in Period)	Experimental	MK-3655 Matching Placebo	Drug	Vial	0 mg	2 x 1.5 mL injections once	SC	V4 up to V5 (Run-in Period)	Placebo	IMP	Provided centrally by the Sponsor
Group 3	Experimental	MK-3655 100 mg/mL	Drug	Vial	300 mg	2 x 1.5 mL injections Q4W	SC	V5 to V15 (Double-Blind Treatment Period)	Test Product	IMP	Provided centrally by the Sponsor
Group 4 (Run-in Period)	Placebo Comparator	MK-3655 Matching Placebo	Drug	Vial	0 mg	2 x 1.5 mL injections once	SC	V4 up to V5 (Run-in Period)	Placebo	IMP	Provided centrally by the Sponsor
Group 4	Placebo Comparator	MK-3655 Matching Placebo	Drug	Vial	0 mg	2 x 1.5 mL injections Q4W	SC	V5 to V15 (Double-Blind Treatment Period)	Placebo	IMP	Provided centrally by the Sponsor

Admin=administration; EEA=European Economic Area; IMP=Investigational Medicinal Product; NIMP/AxMP=Non-Investigational Medicinal Product/Auxiliary Medicinal Product; Q4W=once every 4 weeks; SC=subcutaneous; V=visit.

Notes:

The classification of IMP and NIMP/AxMP in this table is based on guidance issued by the European Commission and applies to countries in the EEA. Country differences with respect to the definition/classification of IMP and NIMP/AxMP may exist. In these circumstances, local legislation is followed.

In Japan, administration of study intervention will not be allowed by a caregiver. See Section 8.1.8.3 and Appendix 7.

All supplies indicated in [Table 3](#) will be provided per the "Sourcing" column depending upon local country operational requirements.

Refer to Section 8.1.9 for details regarding administration of the study intervention.

All placebos were created by the Sponsor to match the active product.

6.2 Preparation/Handling/Storage/Accountability

6.2.1 Dose Preparation

There are no specific calculations or evaluations required to be performed in order to administer the proper dose to each participant. The rationale for selection of doses to be used in this study is provided in Section 4.3.

6.2.2 Handling, Storage, and Accountability

The investigator or designee must confirm appropriate temperature conditions have been maintained during transit for all study intervention received, and any discrepancies are reported and resolved before use of the study intervention.

Only participants enrolled in the study may receive study intervention, and only authorized site staff may supply or administer study intervention. All study interventions must be stored in a secure, environmentally controlled, and monitored (manual or automated) area in accordance with the labeled storage conditions with access limited to the investigator and authorized site staff.

The investigator, institution, or the head of the medical institution (where applicable) is responsible for study intervention accountability, reconciliation, and record maintenance (ie, receipt, reconciliation, and final disposition records).

For all study sites, the local country Sponsor personnel or designee will provide appropriate documentation that must be completed for drug accountability and return, or local discard and destruction if appropriate. Where local discard and destruction is appropriate, the investigator is responsible for ensuring that a local discard/destruction procedure is documented.

The study site is responsible for recording the lot number, manufacturer, and expiry date for any locally purchased product (if applicable) as per local guidelines unless otherwise instructed by the Sponsor.

The investigator shall take responsibility for and shall take all steps to maintain appropriate records and ensure appropriate supply, storage, handling, distribution, and usage of study interventions in accordance with the protocol and any applicable laws and regulations.

6.3 Measures to Minimize Bias: Randomization and Blinding

6.3.1 Intervention Assignment

Intervention randomization will occur centrally using an IRT system. There are 4 study intervention arms. Participants will be assigned randomly in a 1:1:1:1 ratio to 1 of 3 doses of MK-3655 study intervention (50 mg Q4W, 100 mg Q4W, or 300 mg Q4W) or a matching placebo study intervention Q4W, respectively.

6.3.2 Stratification

Intervention randomization will be stratified according to the following factors:

1. Concurrent diagnosis of T2DM at the time of randomization (Yes or No)
2. Fibrosis score (Stage 2 or Stage 3)
3. Region (Japan, East Asia excluding Japan, or Other)
 - Japan and East Asia excluding Japan were each added as a separate stratum in region stratification to ensure that randomization of the Japan population and overall East-Asian population (ie, Japan and East Asia excluding Japan) are balanced between-treatment groups. This stratification will allow for an optimal assessment of the Japan subpopulation as required by the regulatory agency, as well as the overall East-Asian population.

If either proportion of participants, those with T2DM or those without T2DM, exceeds approximately 60% of the total targeted sample size, the remaining participants enrolled will be restricted to the other stratum within this stratification factor. **Note:** In Japan, enrollment will not be restricted by this cap, and sites will be able to continue to enroll participants with or without T2DM (see Appendix 7).

6.3.3 Blinding

A double-blinding technique with in-house blinding will be used. All MK-3655 doses and matching placebo will have the same dose volume and be packaged identically so that the blind is maintained. The participant, the investigator, and Sponsor personnel or delegate(s) who are involved in the study intervention administration or clinical evaluation of the participants will be unaware of the intervention assignments.

See Section 8.1.11 for a description of the method of unblinding a participant during the study should such action be warranted.

6.4 Study Intervention Compliance

When participants self-administer study intervention at the site, compliance with study intervention will be assessed by site personnel observation. The date and time of each dose administered in the clinic will be recorded in the source documents, the CRF, and the

participant diary. At all protocol-specified site visits, the investigator or qualified designee is to record whether treatment had been taken per protocol. If not, the date(s) and reason for each dosing noncompliance must be recorded.

When participants self-administer study intervention at home, compliance with study intervention will be assessed at the next site visit. Compliance will be assessed using participant diaries. A visual inspection of the vials returned (used and unused) will also be performed (when available). Deviation(s) from the prescribed dosage regimen will be recorded in the CRF.

A record of the number of vials dispensed to and returned by each participant must be maintained and reconciled with study intervention and compliance records. Intervention start and stop dates, including dates for intervention delays and/or dose reductions will also be recorded in the CRF.

Note: In Japan, administration of study intervention will not be allowed by a caregiver. See Section 8.1.8.3 and Appendix 7.

6.5 Concomitant Therapy

Medications specifically prohibited in the exclusion criteria are not allowed during the study (see Section 5.2). If there is a clinical indication for any medications specifically prohibited, discontinuation from study intervention may be required. Medications required to be stable upon study entry (see [Table 1](#)) that require adjustment during the trial may result in discontinuation. The investigator should discuss any questions regarding this with the Sponsor Clinical Director. The final decision on any supportive therapy rests with the investigator and/or the participant's primary physician. However, the decision to continue the participant on study intervention requires the mutual agreement of the investigator, the Sponsor, and the participant.

Any medication or vaccine (including over-the-counter or prescription medicines, vitamins, and/or herbal supplements or other specific categories of interest) that the participant is receiving at the time of enrollment or receives during the study must be recorded along with:

- Reason for use
- Dates of administration including start and end dates
- Dosage information including dose and frequency

The Medical Monitor or appropriate designee should be contacted if there are any questions regarding concomitant or prior therapy.

6.5.1 Rescue Medications and Supportive Care

No rescue or supportive medications are specified to be used in this study. Participants should receive appropriate supportive care measures as deemed necessary by the treating investigator.

6.6 Dose Modification

Participants will be randomized to a fixed dose regimen of MK-3655 (50 mg Q4W, 100 mg Q4W, or 300 mg Q4W) or matching placebo for the duration of the study. Dose modifications (ie, delays in the administration of study intervention) are permitted if clinically warranted (eg, due to AEs).

6.7 Intervention After the End of the Study

There is no study-specified intervention following the end of the study.

6.8 Clinical Supplies Disclosure

The emergency unblinding call center will use the intervention/randomization schedule for the study to unblind participants and to unmask study intervention identity. The emergency unblinding call center should only be used in cases of emergency (see Section 8.1.11). In the event that the emergency unblinding call center is not available for a given site in this study, the central electronic intervention randomization system (IRT) should be used to unblind participants and to unmask study intervention identity. The Sponsor will not provide random code/disclosure envelopes or lists with the clinical supplies.

6.9 Standard Policies

Not applicable.

7 DISCONTINUATION OF STUDY INTERVENTION AND PARTICIPANT WITHDRAWAL

7.1 Discontinuation of Study Intervention

Discontinuation of study intervention does not represent withdrawal from the study.

As certain data on clinical events beyond study intervention discontinuation may be important to the study, they must be collected through the participant's last scheduled follow-up, even if the participant has discontinued study intervention. Therefore, all participants who discontinue study intervention prior to completion of the protocol-specified treatment period will still continue to participate in the study as specified in Section 1.3 and Section 8.11.6.

Participants may discontinue study intervention at any time for any reason or be discontinued from the study intervention at the discretion of the investigator should any untoward effect occur. In addition, a participant may be discontinued from study intervention by the

investigator or the Sponsor if study intervention is inappropriate, the study plan is violated, or for administrative and/or other safety reasons. Specific details regarding procedures to be performed at study intervention discontinuation are provided in Section 8.1.10 and Section 8.11.6.

A participant must be discontinued from study intervention but should continue to be monitored in the study for any of the following reasons:

1. The participant or participant's legally acceptable representative requests to discontinue study intervention.
2. The participant has a medical condition or personal circumstance, which in the opinion of the investigator and/or Sponsor, placed the participant at unnecessary risk from continued administration of study intervention.
3. The participant has a positive urine pregnancy test and confirmed by positive serum pregnancy test.

Clinical Events

4. The participant has a CTCAE Grade 3 clinical AE that is considered drug-related by the investigator.
5. The participant has any CTCAE Grade 4 clinical AE, unless the investigator and Sponsor concur that the AE is *clearly not* causally related to study intervention and that continuation/resumption of study intervention does not place the participant at unnecessary risk.

The following AEs are exceptions to #4 and #5. For these events, CTCAE severity grading will not be used as a basis for a participant to be discontinued from study intervention. The requirements for a participant to be discontinued from study intervention are listed for each AE.

- **Weight gain**: Participants will be discontinued from study intervention if body weight measured at the study site has increased $\geq 15\%$ from baseline (Visit 5/Randomization) at any time during the study.
- **Obesity**: The CTCAE grading for obesity is not applicable to this study as participants with a BMI of 25.0 kg/m² to 50.0 kg/m² are eligible for study participation (see Section 5.1, inclusion criterion #5). Instead, discontinuation of study intervention will be based on weight gain as described above.
- **Hypoglycemia in participants with T2DM**: A participant with T2DM will be discontinued from study intervention if the participant has repeated (2 or more episodes since the prior visit) FPG or fingerstick glucose < 50 mg/dL (< 2.8 mmol/L) with or without symptoms of hypoglycemia or ≤ 70 mg/dL (≤ 3.9 mmol/L) with symptoms of hypoglycemia, and without a reasonable explanation (such as increased physical activity or skipped meal).

If a participant is taking any concomitant medications known to cause hypoglycemia (ie, insulins, sulfonylureas, and meglitinides), discontinuation of study intervention should occur only if hypoglycemia persists after down-titration and discontinuation of those medications.

Note: The investigator should ensure that the participant's glucose meter is functioning accurately and that the test procedure is being correctly performed by the participant before discontinuation of study intervention.

- Participants known to have hypertension or with a baseline blood pressure >120 mm Hg (systolic) or >80 mm Hg (diastolic) before randomization: Participants known to have hypertension or with a baseline blood pressure >120 mm Hg (systolic) or >80 mm Hg (diastolic) before randomization will be discontinued from study intervention for a persistent increase from baseline of ≥ 20 mm Hg (systolic blood pressure) and/or ≥ 10 mm Hg (diastolic blood pressure) despite continuation of any antihypertensive regimen being used at baseline AND initiation and/or dose increase of >2 anti-hypertensive agents are required for management. Note: Multiple changes made to a single medication (eg, initiation at lower dose followed by dose increase) counts as only one adjustment.

Note: NCI CTCAE, Version 5.0 will not be used for grading AE severity for participants known to have hypertension or with a baseline blood pressure >120 mm Hg (systolic) or >80 mm Hg (diastolic) before randomization. Instead, the investigator will assess AE intensity according to the following modified CTCAE grading:

- Grade 1: Persistent increase from baseline of 10 mm Hg to 19 mm Hg (systolic blood pressure) and/or 5 mm Hg to 9 mm Hg (diastolic blood pressure) despite continuation of any anti-hypertensive regimen being used at baseline.
- Grade 2: Persistent increase from baseline of ≥ 20 mm Hg (systolic blood pressure) and/or ≥ 10 mm Hg (diastolic blood pressure) despite continuation of any anti-hypertensive regimen being used at baseline **AND** initiation and/or dose increase of ≤ 2 anti-hypertensive agents required for management.*
- Grade 3: Persistent increase from baseline of ≥ 20 mm Hg (systolic blood pressure) and/or ≥ 10 mm Hg (diastolic blood pressure) despite continuation of any anti-hypertensive regimen being used at baseline **AND** initiation and/or dose increase of >2 anti-hypertensive agents required for management.*
- Grade 4: Life-threatening consequences (eg, malignant hypertension, transient or permanent neurologic deficit, hypertensive crisis); urgent intervention indicated.
- Grade 5: Death related to AE.

***Note:** Multiple changes made to a single medication (eg, initiation at lower dose followed by dose increase) counts as only one adjustment.

Laboratory Abnormalities

6. The participant has a CTCAE Grade 3 laboratory abnormality considered drug-related by the investigator, if clinically significant medical intervention is required to treat the event **and/or** the abnormality leads to hospitalization.
7. The participant has any CTCAE Grade 4 laboratory abnormality that requires clinically significant medical intervention to treat the event **and/or** the abnormality leads to hospitalization. Continuation/resumption of study medication may be considered if the investigator and Sponsor concur that the abnormality is **clearly not** causally related to study medication and that this does not place the participant at unnecessary risk.

The following laboratory abnormalities are exceptions to #6 and #7. For these events, CTCAE severity grading will not be used as a basis for a participant to be discontinued from study intervention. The requirements for a participant to be discontinued from study intervention are listed for each laboratory abnormality.

- **Abnormalities of ALT and/or AST:** If the participant has abnormal ALT and/or AST meeting criteria specified in Appendix 10 and no other cause for the combination of laboratory abnormalities is immediately apparent (eg, prolonged INR with warfarin use), study intervention will be discontinued.

Note: See Appendix 10 for additional details on management of blinded study intervention for participants with elevated liver enzymes.

- **Reduction of renal function:** If the participant has an eGFR that is persistently $<30 \text{ mL/min/1.73 m}^2$ as calculated by the MDRD formula, study intervention will be discontinued. For participants in Japan, eGFR will be calculated with the Japanese 3-variable Equation 4 (Appendix 7) [Matsuo, S., et al 2009]. See Appendix 13 for the eGFR equations.

Note: A persistent eGFR value is defined as a repeat measurement, performed within 2 weeks after notification from the central laboratory, that remains $<30 \text{ mL/min/1.73 m}^2$, despite correction of potential causative factors (eg, correction of volume depletion, discontinuation of NSAIDs). If the eGFR value continues to meet the discontinuation criterion but demonstrates stability or improvement relative to the prior result, an additional repeat measurement may be performed within 7 days.

- **Salivary cortisol:** If the participant has a bedtime salivary cortisol test value $>1.5 \times \text{ULN}$ **AND** $>50\%$ above baseline during the study, a repeat bedtime salivary cortisol will be obtained. If the second test value is also $>1.5 \times \text{ULN}$ **AND** $>50\%$ above baseline, a 24-hour urinary cortisol test will be performed. If the 24-hour urinary cortisol value is elevated $>1 \times \text{ULN}$, study intervention will be discontinued (see Section 8.3.9.1).

Note: The baseline assessment for the salivary cortisol test value is considered the one closest to but before dosing (Visit 5/Randomization [Day 1]). However, if no sample is collected before the Visit 5/Randomization, the Visit 1/Screening test value should be used for the baseline assessment.

- **TSH, FT4:** If the participant has TSH and/or FT4 values outside the normal range of the assay and any signs or symptoms of hyperthyroidism or hypothyroidism accompany the changes in thyroid function tests, study intervention will be discontinued (see Section 8.3.9.2).
- **IGF-1:** If the participant has 2 sequential IGF-1 values above the age-appropriate ULN of the assay **AND** >30% above baseline during the study, study intervention will be discontinued (see Section 8.3.9.3).

For participants who are discontinued from study intervention but continue to be monitored in the study, all visits and procedures, as outlined in the SoA, should be completed.

Discontinuation from study intervention is “permanent.” Once a participant is discontinued from study intervention, they shall not be allowed to restart study intervention.

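### Section 7.1: for participants entering with hypertension or raised blood pressure, a life-threatening hypertensive event can have no mandatory event-specific stop, while the milder Grade 3 event does

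*Combined protocol and SAP*

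**What the plan says.** Section 7.1 lists the reasons for which study intervention must be stopped. Reason 4 covers drug-related Grade 3 clinical AEs. Reason 5 begins "The participant has any CTCAE Grade 4 clinical AE, unless the investigator and Sponsor concur that the AE is" plainly unrelated to treatment; they must also agree that continuing carries no unnecessary risk.

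Four kinds of event are then taken out of reasons 4 and 5: weight gain, obesity, hypoglycemia in T2DM, and blood pressure in participants with known hypertension or a baseline above 120 systolic or 80 diastolic. The lead-in states "For these events, CTCAE severity grading will not be used as a basis for a participant to be discontinued from study intervention" and adds that the stopping requirement is the one given for each event.

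For the blood pressure group, that requirement has two parts joined by AND:
- a persistent rise from baseline of at least 20 mm Hg systolic and/or 10 mm Hg diastolic despite the baseline regimen; and
- "initiation and/or dose increase of >2 anti-hypertensive agents are required for management".

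The section then gives this group its own severity scale. Modified Grade 3 has the same rise and the same agent count: "initiation and/or dose increase of >2 anti-hypertensive agents required for management". The next level is "Grade 4: Life-threatening consequences (eg, malignant hypertension, transient or permanent neurologic deficit, hypertensive crisis); urgent intervention indicated".

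**The concern.** The exception removes the Grade 4 default and replaces it with a criterion that restates modified Grade 3. The scale goes one level higher, but no listed stop refers to that level. Modified Grade 4 is defined by its consequences and has no persistence or agent-count condition. A life-threatening event can therefore fail the listed stop that a less severe event meets.

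What is lost is the default in reason 5: dosing stops unless two parties agree on both causality and risk. It is lost only for participants who enter with hypertension or raised pressure. Everyone else keeps reason 5 for the same event. The documents give no rationale for dropping it. The liver enzyme exception in the same section is handled differently: its replacement criteria in Appendix 10 keep a severe end (confirmed ALT or AST above 8 × ULN, or at least 500 U/L when baseline was raised).

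**Working it through.** The plan states no figure on this point, so the check is a comparison of rules followed by a dose count.

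**Rule logic.** Let A be the persistent rise of at least 20 and/or 10 mm Hg, and B be more than two agents started or increased. Several changes to one drug count once. The listed stop needs both A and B.

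| Event in the blood pressure group | A | B | Listed stop |
|---|---|---|---|
| Modified Grade 3 | met | met | stop |
| Modified Grade 4, persistent, more than 2 agents | met | met | stop |
| Modified Grade 4, persistent, 1–2 agents | met | not met | none |
| Modified Grade 4, acute and not persistent | not met | either | none |

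In the last two rows the lead-in has already switched off reasons 4 and 5. This conclusion uses the lead-in alone. It does not depend on the later note about CTCAE version 5.0, whose reach is unclear.

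**Other routes.** Sections 6.6, 8.1.10, 8.3.7, 8.3.12, 8.4.7 and 8.11.6 contain no blood pressure stop. Four routes remain, all resting on judgement or of uncertain reach:
- reason 2, a condition "which in the opinion of the investigator and/or Sponsor, placed the participant at unnecessary risk from continued administration of study intervention";
- the general provision that a participant may "be discontinued from the study intervention at the discretion of the investigator should any untoward effect occur";
- Section 6.6: "Dose modifications (ie, delays in the administration of study intervention) are permitted if clinically warranted (eg, due to AEs");
- the sentence in Section 6.5 that makes continuation depend on agreement of investigator, Sponsor and participant. It sits in a paragraph on prohibited and stability-restricted drugs. Table 1 does not name antihypertensives, though its general row on changed prescription medication might reach them.

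**Dose count.** Dosing is every 4 weeks from Week 0 to Week 48 (Section 8.1.9.1).
- Scheduled doses: 48/4 + 1 = 13.
- Event between the Week 0 and Week 4 doses: 13 − 1 = 12 left.
- Event at Week 10: Weeks 12 to 48, (48 − 12)/4 + 1 = 10 left. Three are home doses (Weeks 28, 36, 44) and 10 − 3 = 7 are at site.
- Event after the Week 48 dose: 13 − 13 = 0 left.

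**Worked comparison** (illustrative participants):
- Participant A, baseline 150/88, has a hypertensive crisis at Week 10 controlled with two agents. This is modified Grade 4 with no mandatory event-specific stop and 10 doses still scheduled.
- Participant B, baseline 118/78 and no hypertension, has the same crisis. Reason 5 applies, so dosing stops unless both parties agree otherwise.
- Participant A instead has a sustained 20 mm Hg systolic rise needing three agents. This is modified Grade 3 and dosing must stop.

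**The case against.** The strongest reply is that a mandatory stop survives. Reason 2 is on the same must-stop list, the exceptions do not touch it, and either the investigator or the Sponsor can invoke it alone. A life-threatening event is an SAE reported within 24 hours (Section 8.4.4, Appendix 3), so the Sponsor would nearly always know before the next dose. Reason 5 also involves judgement. This stands as a limit on the practical risk: most investigators would probably use reason 2. But reason 2 stops dosing only if someone forms the opinion, whereas reason 5 stops it unless two parties agree otherwise and also requires a view on causality. That default is what is lost. If the Section 6.5 sentence applies, agreement to continue is already needed, and the loss is the causality test.

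A second reply is that modified Grade 4 was meant to feed reason 5. The lead-in says otherwise, and nothing in the text links the modified scale to reasons 4 or 5. If that was the intent, sites cannot see it.

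A third reply is that the remaining case is narrow. That is correct. A crisis with a persistent rise needing more than two agents does stop, and a consequence recorded as its own Grade 4 AE, such as stroke, is not on the exceptions list.

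The evidence for a blood pressure hazard is also thin. Section 2.2.1 lists blood pressure among effects associated with FGF21, but links those effects to receptors that this antibody is designed to avoid. Section 2.2.2.2 reports no meaningful blood pressure differences in two Phase 1 studies. Their exposures were about 2.1- and 2.6-fold those predicted for 300 mg Q4W (Section 4.3.3). Entry pressure is capped at 160/90, readings are in triplicate at site visits, serious CV events are adjudicated, and the eDMC reviews safety.

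Home dosing adds little. The calls at those weeks do not list blood pressure (Section 8.1.8.8), but they do record AEs and medications, and the gap concerns what happens after a crisis has been recognised.

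**Conclusion.** The concern holds. As written, Section 7.1 gives an inverted result in this subgroup: a modified Grade 3 event requires a stop, while a modified Grade 4 event that is acute or managed with one or two agents does not, unless someone invokes a judgement-based route.

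The exposure at stake is 0 to 12 of 13 doses, depending on timing, and 10 after a Week 10 event. These counts are upper limits: they assume that nobody uses reason 2, discretion or a dose delay. The documents give neither an event rate nor the size of the subgroup, and none is assumed; that such events are rare is a judgement. Other safeguards remain, and the primary analysis, power and error control are not affected. The point should be fixed because the event is life-threatening, the wording is explicit, and the correction is small.

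**What to change.** Add to the hypertension bullet in Section 7.1: *A modified Grade 4 event remains subject to #5.* Change the lead-in to match, for example: *The following AEs are exceptions to #4 and #5 (except modified Grade 4 hypertension, which remains subject to #5).*

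This is one sentence and one edit, by amendment or clarification letter. The cost is possibly a few more treatment discontinuations, which Section 7.1 makes permanent. The opt-out in reason 5 for plainly unrelated events limits that number. Participants who stop stay in follow-up under Section 8.11.6, so no new procedures or data are needed.
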